- Amount of IP to be shipped to site for the IP administration on Day 390 (Visit 20) will be based on the measurement of body weight obtained at this visit. Body weight measurement must be verified by two site personnel and entered into the interactive response technology drug management system to trigger IP shipment to the site. This visit is not applicable for Cohort 1 participants confirmed to meet exclusion criterion 15 (see [Section 5.2](#)).

Period	Screening	Baseline	Main Study Period (Year 1)																				Early Discontinuation Visit ^g
			Visit 1 ^a	Visit 2 ^c	Visit 3 ^d	Visit 4	Visit 5	Visit 6	Visit 7	Visit 8 & 9	Visit 10	Visit 11	Visit 12 ^e	Visit 12.2	Visit 13	Visit 13.1 ^{kk}	Visit 13.2 ^e	Visit 14 ^b	Visit 14.2 ^e	Visit 15 ^e	Visit 16	Visit 17	Visit 18 ^f
Visit Number/ Description	Visit 1 ^a	Visit 2 ^c	Week 1, Day 1	Week 1, Day 2	Week 1, Day 4	Week 1, Day 6	Week 1, Day 7	Week 2, Day 8 & 9	Week 2, Day 10	Week 2, Day 14	Week 3	Week 4	Week 5	Week 6	Week 7	Week 9	Week 11	Week 13	Week 18	Week 35	Week 47	Week 52	
	Screening	Baseline																					
Visit Day	-90 to -30	-48 to -16	1	2	4	6	7	8 & 9	10	14	21	28	34	42	48	60	74	90	120	240	328	360	
Visit Window (± days)			0	0	0	0	0	0	0	1	1	1	1	3	3	3	3	7	7	14	7		

- For participants who undergo Day 328 (Visit 18) during a study dosing pause, the amount of IP to be shipped to the site will be determined once the study has been restarted. Therefore, the weight collected at Day 328 (Visit 18) will not be entered into the interactive response technology drug management system during the dosing pause. Participants will be evaluated for Year 2 IP eligibility when the study is restarted.
- May not be applicable for participants confirmed to meet exclusion criterion 15 or those who declined Year 2 IP administration (see [Appendix 12](#) and [Section 7.2.1](#)).

g. **Early Discontinuation Visit**

- This visit is not applicable for participants who withdraw prior to Day 1 (Visit 3) or for Cohort 2 participants who are withdrawn from the study between Day 360 (Visit 19) and Day 390 (Visit 20) (see [Section 7.1](#)).
- The site will contact the Sponsor to determine which laboratory (blood) tests should be collected at the Early Discontinuation Visit, to ensure that the daily and 4-week maximum blood volume limits are not exceeded.
- CBCL questionnaire: Only if the previous CBCL questionnaire was completed more than 2 months before the date of the Early Discontinuation Visit.
- NAb to AAV9, ADA to mini-dystrophin and AAV9, ELISpot to mini-dystrophin and AAV9: Only if the participant discontinues the study before Visit 37 (Year 3, Day 1110).
- Clinical safety: Only if the previous analysis had been done more than 1 month before the date of the Early Discontinuation visit.
- Echocardiogram: Only if the previous echocardiogram had been done more than 6 months before the date of the Early Discontinuation Visit.
- FVC: Only if the previous FVC had been assessed more than 2 months before the date of the Early Discontinuation Visit.
- Viral vector shedding: For any given matrix, if the sample(s) had still been collected at the participant's last study visit, it should also be collected at the Early Discontinuation Visit.

h. **Brief physical and neurological examinations**, as described in [Section 8.2](#), are acceptable post-baseline unless safety concerns warrant full examination.

i. **O2 saturation** will only be measured before the start of the IP infusion and during the inpatient stay post IP administration.

j. **Vital signs** will be measured 3 times per day during the inpatient stay post IP administration.

Period	Screening	Baseline	Main Study Period (Year 1)																					Early Discontinuation Visit ^g
			Visit 1 ^a	Visit 2 ^c	Visit 3 ^d	Visit 4	Visit 5	Visit 6	Visit 7	Visit 8 & 9	Visit 10	Visit 11	Visit 12 ^e	Visit 12.2	Visit 13	Visit 13.1 ^{kk}	Visit 13.2 ^e	Visit 14 ^b	Visit 14.2 ^e	Visit 15 ^e	Visit 16	Visit 17	Visit 18 ^f	
Visit Number/ Description	Visit 1 ^a	Visit 2 ^c	Week 1, Day 1	Week 1, Day 2	Week 1, Day 4	Week 1, Day 6	Week 1, Day 7	Week 2, Day 8 & 9	Week 2, Day 10	Week 2, Day 14	Week 3	Week 4	Week 5	Week 6	Week 7	Week 9	Week 11	Week 13	Week 18	Week 35	Week 47	Week 52		
	Screening	Baseline																						
Visit Day	-90 to -30	-48 to -16	1	2	4	6	7	8 & 9	10	14	21	28	34	42	48	60	74	90	120	240	328	360		
Visit Window (± days)			0	0	0	0	0	0	0	1	1	1	1	3	3	3	3	7	7	14	7			

k. **12-Lead ECG** will be collected and read locally for immediate interpretation and safety monitoring and will be submitted to a central laboratory for standardized interpretation.

- l. **Clinical laboratory tests** are described in detail in [Table 3 \(Appendix 2\)](#).
 - For urinalysis, a microscopic analysis will be performed only if urine dipstick is positive for blood, protein, nitrites or leukocyte esterase.
 - On the following visits: Baseline Visit (Visit 2), Day 60 (Visit 14), Day 120 (Visit 16), Day 240 (Visit 17) and Day 360 (Visit 19), in which functional assessments (eg, NSAA) are performed, blood draws should always be done first, whenever possible, to ensure that the CK levels are obtained prior to the functional test; for additional advice regarding the ordering of assessments please consult the Functional Assessment Manual.
- m. **Banked biospecimens for biomarkers** are collected as described in [Section 8.8.4](#).
- n. **Banked biospecimens for genetics** are collected as described in [Section 8.7.2](#).
- o. **Open muscle biopsies** will be obtained in approximately the first 15 participants randomized into Cohorts 1 and 2, and their siblings, at sites that have been trained and certified by the Sponsor/Sponsor designee to collect open muscle biopsies, following administration of an anesthetic (eg, regional block or under general anesthesia) according to institutional standard practice, and only after any imaging and functional assessments scheduled for the same visit have been completed. Baseline visit muscle biopsies will be performed after randomization. If a muscle biopsy cannot be scheduled on the day of the Baseline Visit, the biopsy may be performed at a later day, as long as it is at least 2 weeks before dosing.
- p. **Echocardiograms** will be collected and read locally for immediate interpretation and safety monitoring and will be submitted to a central laboratory for standardized interpretation.
- q. The **NSAA and CGIS** will be administered by a single clinical evaluator at each visit and whenever possible, the same CE should administer the functional assessments (NSAA, ankle range of motion and FVC) for the same participant throughout the study. The NSAA, ankle range of motion and FVC may be video recorded at the Day 1 (Screening Visit), Baseline Visit (Visit 2), and at the annual visits (ie, Visits 19, 35, 37, 39, 41, 43). If CE re-training is required, the assigned master physiotherapist may request additional visits to be recorded and reviewed. Whenever possible, motor functional assessments should be performed early in the course of the visit, to help reduce the effect of fatigue on the participants' performance; for additional advice regarding the ordering of assessments please consult the Functional Assessment Manual.
- r. **Ambulatory assessment** at Screening (Visit 1) is based only on the ability to perform the 10 m run/walk, as assessed during the NSAA.

Period	Screening	Baseline	Main Study Period (Year 1)																					Early Discontinuation Visit ^a
			Visit 1 ^a	Visit 2 ^c	Visit 3 ^d	Visit 4	Visit 5	Visit 6	Visit 7	Visit 8 & 9	Visit 10	Visit 11	Visit 12 ^e	Visit 12.2	Visit 13	Visit 13.1 ^{kk}	Visit 13.2 ^e	Visit 14 ^b	Visit 14.2 ^e	Visit 15 ^e	Visit 16	Visit 17	Visit 18 ^f	
Visit Number/ Description	Visit 1 ^a	Visit 2 ^c	Week 1, Day 1	Week 1, Day 2	Week 1, Day 4	Week 1, Day 6	Week 1, Day 7	Week 2, Day 8 & 9	Week 2, Day 10	Week 2, Day 14	Week 2, Day 14	Week 3	Week 4	Week 5	Week 6	Week 7	Week 9	Week 11	Week 13	Week 18	Week 35	Week 47	Week 52	Week 52
	Screening	Baseline																						
Visit Day	-90 to -30	-48 to -16	1	2	4	6	7	8 & 9	10	14	21	28	34	42	48	60	74	90	120	240	328	360		
Visit Window (± days)			0	0	0	0	0	0	0	1	1	1	1	3	3	3	3	3	7	7	14	7		

s. An activity monitor will be placed on the participant's ankle prior to the performing of other functional assessments and is to be worn continuously for the subsequent 2 weeks.

t. COAs will be completed by the caregiver on behalf of the participant and/or by the participants themselves, depending on the participant's age and at the discretion of the Investigator and caregiver, as described in [Section 8.1.7](#).

u. Starting on Day 1 (Visit 3) participants will not take their background **glucocorticoid regimen**. Participants will replace their background glucocorticoid regimen with the protocol-mandated glucocorticoid regimen for 90 days post-IP administration, after which, as long as there is no immune response or other clinical indication, participants may return to their background glucocorticoid regimen (see [Section 6.5.1](#)).

v. For eligibility for Year 1 IP administration please see [Section 6.1.1](#).

w. For details regarding post IP intensified safety monitoring please see [Section 8.2.10](#). For sites in Japan: haptoglobin will be analyzed by the local laboratory on Days 2 and 4 (Visits 4 and 5).

x. All participant who has a muscle biopsy at the Baseline Visit (Visit 2), and their siblings, will undergo 2 post-Baseline muscle biopsies. The post Baseline muscle biopsies will be performed on Day 360 (Visit 19) in Year 1 and on Day 1830 (Visit 41) during Long Term Follow-Up. If the post-baseline muscle biopsy cannot be performed on the scheduled day, the biopsy may be performed at a later day, as long as it is at least 2 weeks before dosing for the biopsy at Visit 19 and within 1 month of the day of the visit for the biopsy at Visit 41.

y. FVC will be assessed throughout the study on participants who are ≥6 years old at Screening. Participants <6 years old at the Screening Visit (Visit 1) will not have FVC evaluated at any time during the study.

z. Viral vector shedding will be measured in approximately the first 45 treated participants (approximately 30 treated with fordadistrogene movaparvovec and approximately 15 treated with placebo) only after IP administration, as described in [Section 8.8.5](#). For each of the approximately 45 first treated participants, sample collection for a particular matrix (sample type) will be stopped when at least 2 consecutive negative results are observed in that matrix. See [Section 8.8.5](#) for additional details.

aa. Urine and some blood samples will be collected for local laboratory testing to ensure fast turnaround of test results. Some blood samples ie, GLDH at Visit 9 will be sent to the central laboratory to prevent sharing the results of ALT/AST sensitive clinical data. C3/C4 will also be sent to the central laboratory at Visits 6, 7, 8, 9, and 10. For more details, please see [Section 8.2.12](#) and [Appendix 2](#). For sites in Japan only: additional local laboratory tests will be collected at Visits 4 and 5, see [Appendix 2](#) for details.

bb. In order to ensure an adequate understanding and management of potential safety risks, the initial rate of randomization into the study will be limited. No more than 2 participants per week will be randomized at the start of the study, until 4 participants have been observed for at least 2 weeks post IP administration. After that, the rate could

Period	Screening	Baseline	Main Study Period (Year 1)																					Early Discontinuation Visit ^g	
			Visit 1 ^a	Visit 2 ^c	Visit 3 ^d	Visit 4	Visit 5	Visit 6	Visit 7	Visit 8 & 9	Visit 10	Visit 11	Visit 12.2	Visit 13	Visit 13.1 ^{kk}	Visit 13.2 ^e	Visit 14 ^b	Visit 14.2 ^e	Visit 15 ^e	Visit 16	Visit 17	Visit 18 ^f	Visit 19 ^b		
Visit Number/ Description	Visit 1 ^a	Visit 2 ^c	Screening	Baseline	Wee k 1, Day 1	Wee k 1, Day 2	Wee k 1, Day 4	Wee k 1, Day 6	Wee k 1, Day 7	Wee k 2, Day 8 & 9	Wee k 2, Day 10	Wee k 2, Day 14	Wee k 3	Wee k 4	Week 5	Week 6	Week 7	Wee k 9	Wee k 11	Wee k 13	Wee k 18	Wee k 35	Wee k 47	Wee k 52	Early Discontinuation Visit ^g
Visit Day	-90 to -30	-48 to -16	1	2	4	6	7	8 & 9	10	14	21	28	34	42	48	60	74	90	120	240	328	360			
Visit Window (± days)			0	0	0	0	0	0	0	1	1	1	1	3	3	3	3	3	7	7	14	7			

be increased to no more than 3 participants randomized per week (until a total of 10 participants have been observed for at least 2 weeks post-IP administration). Thereafter, the rate of randomization could be further increased to no more than 5 participants randomized per week (until a total of 20 participants have been observed for at least 2 weeks post-IP administration). After this time, no limits of the randomization rate will be imposed unless the study team, in consultation with the E-DMC, determines otherwise. For more details- please see [Section 4.1](#).

- cc. The NAb to AAV9 blood samples at the Baseline Visit (Visit 2) will always be collected and sent to the Central Laboratory, but will only be analyzed and reviewed prior to Day 1 Visit (Visit 3) if the time between the first blood draw for NAb to AAV9 testing at the Screening Visit (Visit 1) or most recent test, if repeat blood draw(s) was required, and the Day 1 Visit (Visit 3) is expected to be more than 55 days, which is anticipated to occur rarely. Dosing cannot occur unless there is a negative test to AAV9 from a sample collected 55 or less days before the day of IP administration.
- dd. For US sites, only when approved by the relevant Institutional Review Board.
- ee. On Day 28 (Visit 12.2), only GLDH will be collected.
- ff. ADA to mini-dystrophin only.
- gg. The Investigator will discuss with the participant and caregiver the importance of having a baseline cardiac MRI, even under general anesthesia to be able to assess and manage potential cardiac adverse events during the study. This discussion and the decision to perform or not a baseline cardiac MRI will be documented in the participant's records. A Participant requiring anesthesia or unable to undergo investigation with closed MRI (eg, metal implants) may be exempt, and will be allowed to be randomized in the study without a cardiac MRI. Sites will be responsible for confirming participant eligibility to undergo MRI scanning and gadolinium contrast administration ([Section 2.3.3.7](#)). If the site considers gadolinium contrast administration unsafe, or if the participant has a history of allergy to gadolinium, cardiac MRI without contrast administration will be performed. It is important that the investigator discusses with the participant and/or caregivers that a cardiac MRI even under general anesthesia may be required in certain situations ([Section 8.2.8](#)).
- hh. Cardiac MRI may be performed at any time between the first day of the Screening Visit (Visit 1) and the Day 1 Visit (Visit 3), and after randomization, as long as it is done before Day 1 (Visit 3). If a prior cardiac MRI was performed within 6 months of the Screening Visit (with gadolinium, or without gadolinium if contrast administration is contraindicated), and results are available, then a cardiac MRI at screening will not be performed. Only participants with a pre-IP administration cardiac MRI will have a follow-up cardiac MRI on Day 360 (Visit 19) and on Day 749 (Visit 35).
- ii. Participants will be assessed by a cardiologist at the Screening Visit, see [Section 5.2](#), exclusion criteria 16 and 17.

Period	Screening	Baseline	Main Study Period (Year 1)																					Early Discontinuation Visit ^{aa}
			Visit 1 ^a	Visit 2 ^c	Visit 3 ^d	Visit 4	Visit 5	Visit 6	Visit 7	Visit 8 & 9	Visit 10	Visit 11	Visit 12 ^e	Visit 12.2	Visit 13	Visit 13.1 ^{kk}	Visit 13.2 ^e	Visit 14 ^b	Visit 14.2 ^e	Visit 15 ^e	Visit 16	Visit 17	Visit 18 ^f	
Visit Number/ Description	Visit 1 ^a	Visit 2 ^c	Week 1, Day 1	Week 1, Day 2	Week 1, Day 4	Week 1, Day 6	Week 1, Day 7	Week 2, Day 8 & 9	Week 2, Day 10	Week 2, Day 14	Week 3	Week 4	Week 5	Week 6	Week 7	Week 9	Week 11	Week 13	Week 18	Week 35	Week 47	Week 52	Week 52	
	Screening	Baseline																						
Visit Day	-90 to -30	-48 to -16	1	2	4	6	7	8 & 9	10	14	21	28	34	42	48	60	74	90	120	240	328	360		
Visit Window (± days)			0	0	0	0	0	0	0	1	1	1	1	3	3	3	3	7	7	14	7			

jj. Following IP administration, participants will remain as inpatients for at least 7 days after the infusion has terminated and will be discharged on Day 8, or later if deemed necessary by the Investigator (see [Section 8.2.10](#)).

kk. This visit is for sites in Germany only. Unless clinical concern and/or participant preference and/or the site's institutional review board's preference warrants in-person visit, this visit may be performed remotely, and would include blood collection at or close to the participant's home coordinated by local phlebotomist, as well as phone communication between site staff and participant/caregiver to discuss any adverse events and/or changes to concomitant medications.

ll. Cardiac troponin I or T will be analyzed by the local laboratory only on Day 8 (Visit 8).

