- Unplanned Visit: If the 90-day period between screening and dosing is exceeded due to operational or administrative reasons (eg, enrollment pause due to regulatory or safety review, operational issues causing significant delays), participants will not be screened failed/withdrawn from the study, but will repeat some tests and assessments to re-confirm study/IP administration eligibility criteria, and to rule out significant changes in key tests and assessments (see Sections [5.3](#) and [5.6](#)).

Period	Screening	Baseline	Main Study Period (Year 1)																					Early Discontinuation Visit ^a
			Visit 1 ^a	Visit 2 ^c	Visit 3 ^d	Visit 4	Visit 5	Visit 6	Visit 7	Visit 8 & 9	Visit 10	Visit 11	Visit 12 ^e	Visit 12.2	Visit 13	Visit 13.1 ^{kk}	Visit 13.2 ^e	Visit 14 ^b	Visit 14.2 ^e	Visit 15 ^e	Visit 16	Visit 17	Visit 18 ^f	
Visit Number/ Description	Visit 1 ^a	Visit 2 ^c	Week 1, Day 1	Week 1, Day 2	Week 1, Day 4	Week 1, Day 6	Week 1, Day 7	Week 2, Day 8 & 9	Week 2, Day 10	Week 2, Day 14	Week 2, Day 14	Week 3	Week 4	Week 5	Week 6	Week 7	Week 9	Week 11	Week 13	Week 18	Week 35	Week 47	Week 52	Visit 19 ^b
	Screening	Baseline																						
Visit Day	-90 to -30	-48 to -16	1	2	4	6	7	8 & 9	10	14	21	28	34	42	48	60	74	90	120	240	328	360		
Visit Window (± days)			0	0	0	0	0	0	0	1	1	1	1	3	3	3	3	3	7	7	14	7		

b. Visit 14 and Visit 19 must be conducted in the course of two (preferably consecutive) days in order to comply with daily blood volume limits. Unless clinical concern and/or participant preference and/or the site's institutional review board's preference warrants in-person visit, the follow-up day visit, on the second day, to complete blood collection, may be performed remotely, to allow blood collection at or close to the participant's home. The following laboratory samples must be collected:

Visit 14 (Week 9)

First day: ELISpot to mini-dystrophin and AAV9, viral vector shedding.

Second day: clinical safety, cardiac troponin I, biomarker (creatinine kinase).

Visit 19 (Week 52)

First day: anti-HAV immunoglobulin M, Hepatitis B surface antigen, Hepatitis C antibody (these tests will not be applicable for Cohort 1 participants confirmed to meet exclusion criterion 15 [see Section 5.2]), NAb to AAV9, ADA to mini-dystrophin and AAV9, banked biospecimens for biomarkers, viral vector shedding.

Second day: clinical safety, INR, cardiac troponin I, biomarker (creatinine kinase).

c. Visit 2 – Baseline Visit

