Visit Window (\pm days)	3 ^f	2 ^f	2 ^f	2 ^f	2 ^f	2 ^f	2 ^f	3 ^f	3 ^f	3 ^f	3 ^f	3 ^f	3 ^f	3 ^f	3 ^f	3 ^f	7 ^f	7 ^f	7 ^f	30 ^f	30 ^f		

- If, due to operational or administrative reasons (eg, enrollment pause due to regulatory or safety review, operational issues causing significant delays), a participant's Year 2 IP administration must be delayed, the Day 390 (Visit 20) and also subsequent visits will be delayed for that participant until the pause is lifted. If the pause is not lifted within 6 months of the Day 360 (Visit 19), the participant will undergo an unplanned visit for general monitoring on Day 540 ± 7 days, and approximately every 6 months afterwards until the pause is lifted (or more frequently if considered necessary by the investigator) for sites in Israel, see [Appendix 16](#).

b. Visits 29, 29.2, 30.2, 31.2, and 32

- Unless clinical concern and/or participant preference and/or the site's institutional review board's preference warrants in-person visit, this visit may be performed remotely, and would include blood collection at or close to the participant's home coordinated by local phlebotomist, as well as phone communication between site staff and participant/caregiver to discuss any adverse events and/or changes to concomitant medications.

c. Visit 31 must be conducted in the course of two (preferably consecutive) days in order to comply with daily blood volume limits. Unless clinical concern and/or participant preference and/or the site's institutional review board's preference warrants in-person visit, the follow-up day visit, on the second day, to complete blood collection, may be performed remotely, to allow blood collection at or close to the participant's home. The following laboratory assessments must be collected as follows:

- Visit 31 (Year 2, Week 9)
 - First day: ELISpot to mini-dystrophin and AAV9, viral vector shedding.
 - Second day: clinical safety, cardiac troponin I, biomarker (creatinine kinase).

d. Visit 42 and 43 – Long-term follow up Year 6

- All participants will be followed for 5 years after receiving fordadistrogene movaparvovec. Therefore Visits 42 and 43 only apply to participants randomized to Cohort 2.

e. Early Discontinuation Visit

- This visit is not applicable for Cohort 2 participants who were withdrawn from the study between Day 360 (Visit 19) and Day 390 (Visit 20) (see [Section 7](#)).

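### At Visits 14, 19 and 31 the protocol puts CK on the second visit day but also wants CK drawn before the functional test; with a remote second day both cannot be followed

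*Protocol*

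**What the plan says.** Section 10.10.1.1 (Year 1 Schedule of Activities), footnote b, states that "Visit 14 and Visit 19 must be conducted in the course of two (preferably consecutive) days" to keep within daily blood volume limits. It then fixes which samples belong to which day. At Visit 19 the later list is "Second day: clinical safety, INR, cardiac troponin I, biomarker (creatinine kinase"; at Visit 14 CK is also on the second day. Section 10.10.1.2 (Year 2), footnote c, says that "Visit 31 must be conducted in the course of two (preferably consecutive) days" and gives the later list as "Second day: clinical safety, cardiac troponin I, biomarker (creatinine kinase". The nature of that later day is described in the same footnotes: "the follow-up day visit, on the second day, to complete blood collection, may be performed remotely".

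Footnote l of Section 10.10.1.1 sets a second rule for the visits with functional testing: "blood draws should always be done first, whenever possible, to ensure that the CK levels are obtained prior to the functional test". The Year 1 visits it names are Baseline (Visit 2) and "Day 60 (Visit 14), Day 120 (Visit 16), Day 240 (Visit 17) and Day 360 (Visit 19". Footnote n of Section 10.10.1.2 repeats the rule for Visits 31, 33, 34 and 35.

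Two further ordering rules bear on this. Footnotes q and n ask for motor testing early in the visit, where feasible, to limit fatigue. Footnote o allows a muscle biopsy "only after any imaging and functional assessments scheduled for the same visit have been completed". The same pairs of footnotes recur in the Germany, Russia and Israel schedules (Sections 10.14.1 and 10.14.2, 10.15.1 and 10.15.2, 10.16.1 and 10.16.2).

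**The concern.** The purpose of the blood-first rule is a CK value not raised by the exertion of the test. At three visits the sample lists hold CK back to a day that is laid out for blood collection only. If the NSAA has been done on the first day, the CK value is a post-exercise one, however carefully the site orders its work on either day.

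The Baseline visit is not split, so Baseline CK can be drawn before exercise. A change from Baseline at Week 9 or Week 52 of Year 1 may then compare two different sampling conditions. Whether it does depends on the site's choice of a remote or in-person second day and on the day of the NSAA, so the condition varies within and between participants. CK also serves safety: Appendix 17, in its entry for Amendment 6, gives monitoring of muscle injury by the unblinded medical monitor as the reason for adding other CK draws. Exercise-related variation makes that signal harder to read.

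**Working it through.** No sample size, power or error rate is involved, and the protocol gives no figure to reproduce. The check sets the rules side by side.

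**Visits under the CK-first rule.** Year 1: Visits 2, 14, 16, 17 and 19, five visits (footnote l). Year 2: Visits 31, 33, 34 and 35, four visits (footnote n). Total 5 + 4 = 9.

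**Of these, visits split over two days with CK on the second.** Visits 14 and 19 (footnote b) and Visit 31 (footnote c): 2 + 1 = 3. The other 9 − 3 = 6, including Baseline, have no split, so the conflict does not arise there.

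**What can happen at a split visit:**

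| Second day | Day of NSAA | Order of CK and NSAA | CK-first aim met? |
|---|---|---|---|
| Remote draw | First (the NSAA needs the site evaluator) | NSAA, then CK | No |
| In person | First | NSAA, then CK | No |
| In person | Second, after the draw | CK, then NSAA | Yes |

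The rule fails in two of the three arrangements, and failure is unavoidable in the first, which the protocol permits by default unless clinical concern, participant preference or the review board calls for attendance. The third satisfies both footnotes. It sits awkwardly with testing early in the visit and with a second day meant for completing blood collection, but it is allowed.

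**Does drawing other blood ahead of a first-day NSAA meet the rule?** A site could draw the first-day samples before the NSAA. At Visits 14 and 31 these are ELISpot and viral shedding; at Visit 19 they are hepatitis serology, antibody, banked and shedding samples. None of these lists contains CK, the analyte for which the rule exists.

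**Biopsy.** The Visit 19 biopsy has to follow any functional testing at that visit, but footnote x lets it be done on a later day, at least 2 weeks before dosing, and no visit day is assigned to it. CK may follow a biopsy in some participants; the text does not make this certain. It concerns Visit 19 only, among approximately the first 15 participants randomized and their siblings.

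**The case against.** The strongest reply is that the blood-first rule is qualified by what is feasible, that no shown passage assigns the NSAA to either day, and that the day lists cover laboratory samples only. Sites can comply with everything by bringing the participant back in person and testing after the draw. The order may also be settled in the Functional Assessment Manual, to which the footnotes refer, or in Sections 1.3 and 8 of the protocol, which are not in the part at hand. This stands, and it limits the point: the rule can be met. It does not remove the conflict, because the feasibility qualifier excuses a difficulty at a site, whereas here the schedule itself assigns CK to the later day and allows that day to be remote.

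A reader might go further and infer that the Week 52 CK comparison is biased in favour of one arm. The documents do not support that. Both cohorts follow the same Year 1 schedule, so a bias needs the exercise-related rise in CK to differ between treated and untreated muscle. That is conceivable, but no figure in the protocol bears on it, and any size quoted would only restate an assumption. The part at hand also does not show how CK enters the endpoints.

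Two other extensions fail. Year 2 Week 52 (Visit 35) is not split. The long-term visits that footnote w of Section 10.10.1.2 splits when ELISpot is taken are not on the CK-first list, so no stated rule is broken there.

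**Conclusion.** The point holds as a clash between stated rules, confined to Visits 14, 19 and 31: three of the nine visits under the CK-first rule. The aim of that rule is defeated whenever the NSAA falls on the first day, and unavoidably so when the second day is remote. The supportable consequences are a change from Baseline in CK that mixes sampling conditions, and added noise in CK-based muscle-injury monitoring. Their size cannot be stated: the protocol gives neither the rise in CK after an NSAA nor the share of second days done remotely.

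The conclusion rests on two assumptions: that the NSAA cannot be given at a remote blood draw, and that nothing in Sections 1.3 or 8 or in the Functional Assessment Manual already settles the order.

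**What to change.** Reconcile footnotes b and c with footnotes l and n in every country schedule by requiring the CK sample before the NSAA and, at Visit 19, before any biopsy. Two routes achieve this.

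- **CK on the first day, ahead of functional testing.** At Visit 19, exchange an equal volume of first-day serology or banked samples to the second day. Banked samples are the simpler choice, since hepatitis serology at that visit does not apply to Cohort 1 participants who meet exclusion criterion 15. At Visits 14 and 31 the first day holds only ELISpot and shedding samples, so first confirm that the small CK volume fits the daily limit beside them.
- **NSAA on the second day, after the draw**, where that day is in person. This needs a line saying how it fits with testing early in the visit.

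For data already collected, flag CK values drawn after the NSAA or after a biopsy and repeat the CK summary without them. This requires the date and time of the draw, the NSAA and the biopsy.

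The cost is a footnote and laboratory-manual change, a check of tube allocation against daily blood limits (the text at hand gives no volumes by day), and a small sensitivity analysis. Footnote w needs no change.
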